12.4.4. Appendix 4A: Additional Endpoint Information

All the PET imaging variables are derived by the PET imaging centre and not the responsibility of S&P.

12.4.5. Evaluation of PET Images

The acquired PET information is reconstructed into PET images with due corrections for attenuation, scattered radiation, etc.

The PET images are visually reviewed to identify the general features of body distribution and especially anatomical localization in the heart.

Regions of Interest (RoI) are outlined in the images to define radioactivity distribution.

All organ and blood analyses are expressed as SUV (Measured radioactivity concentration corrected for radioactive decay and normalized for administered amount of radioactivity per body weight).

Depending on organ and selection of tissue components, SUV may have different definitions.

Local tissue radioactivity concentration in organs in Regions of Interest (RoI)

SUV_{peak}:

A small sphere of 10-12 mm diameter placed in a representative location as seen in the image or transferred from the CT scan. Average of voxel (picture element) values within this volume is calculated.

SUV_{mean}:

A larger outline of the whole organ or representative area or volume as seen in the image or transferred from the CT scan. Average voxel values (picture elements) within this volume is calculated.

Total organ radioactivity amount in Regions of Interest (RoI)

SUV_{total organ}:

An outline of the whole volume of the organ attempting to capture the total amount of radioactivity in that organ, as defined in the PET images or transferred from CT scan. Average of voxel (picture element) values within this volume is calculated.

VOLUME_{total organ}:

Corresponding total volume of the organs above.

The SUV_{total organ} and VOLUME_{total organ} are used for calculation of fraction of administered dose in that organ.

The organs/tissues of interest for analysis include:

Local tissue radioactivity concentration in organs in Regions of Interest (RoI)

Where relevant and depending on radioactivity uptake pattern:

- A minimum of 5 anatomical positions within the heart (only in the specific heart scans)
- Up to 3 focal and 1 larger location in each of the lungs
- Up to 3 focal and 1 larger location in the liver
- One focal and one large area in spleen
- One focal and one large area in pancreas
- One cortex and one medulla focal area in each of the kidneys
- One large area in one thigh muscle
- Up to 5 small areas of the skin

Other focal or larger areas may be included depending on features in the images.

For the regions in the 4*5 scans focused over the heart, separate and average values will be generated for each of the Rols.

Total organ radioactivity amount in Regions of Interest (RoI)

- Heart
- Liver
- Spleen
- One lung
- Each kidney

Other organs may be included depending on features in the images.

Analysis of PET Data

The tissue SUV and plasma radio-PK values generated will constitute the primary information from the studies. Since plasma radio-PK will be dependent upon time after administration plus mass dose, it will be necessary to relate the tissue SUV to the instant and possibly also to the AUC of the plasma radio-PK.

It is expected that the tissue-to-plasma ratio of the mAb in the heart will be approximately 0.1-0.2 after equilibration between plasma and tissue interstitium. This is guided by an expected plasma

space plus interstitium relative space of 0.1-0.2. Within the blood pool of the heart chambers the ratio is expected to be 0.5 (hematocrit about 0.5).

We have placed a limit by which the tissue-to-plasma ratio in the cardiac muscle is indicative of entry to the interstitium and binding to amyloid-SAP complexes at 0.5 in balance between a sufficient increase as compared to passive distribution and avoidance of “spill-over” from cardiac blood pools.

More complex models of distribution between plasma and tissue may be explored.

Storage and potential further analyses of images

The primary PET and CT images in digital form will be anonymized and stored in an image repository under the control of GSK and may be used for further analyses.

12.5. Appendix 5: Derived and Transformed Data

12.5.1. General

Multiple Measurements at One Analysis Time Point

 • Mean of the measurements will be calculated and used in any derivation of summary statistics but if listed, all data will be presented. • Subjects having both High and Low values for Normal Ranges at any post-baseline visits for safety parameters will be counted in both the High and Low categories of “Any visit post-baseline” row of related summary tables. This will also be applicable to relevant Potential Clinical Importance summary tables.
Study Day

 • Calculated as the number of days from the first study dose of aSAP treatment (GSK2315698 or labelled mAb or unlabelled mAb): 
 • Ref Date or Study Dose Date = Missing → Study Day = Missing • Ref Date < aSAP treatment first study Dose Date → Study Day = Ref Date – aSAP treatment First Study Dose Date • Ref Data ≥ aSAP treatment first study dose date Dose Date → Study Day = Ref Date – (aSAP treatment First Study Dose Date) + 1

12.5.2. Study Population

Demographics
Age

 • GSK standard IDSL algorithms will be used for calculating age where birth date will be imputed as follows: 
 ○ Any subject with a missing day will have this imputed as day ‘15’. ○ Any subject with a missing date and month will have this imputed as ‘30th June’. • Birth date will be presented in listings as ‘YYYY’.
Body Mass Index
Calculated as Weight (kg) / [Height (m)²]

Extent of Exposure

 Number of days of exposure to CPHPC will be calculated based on the following formula in each Treatment Session: Duration of Exposure in Days = Treatment Stop Date – (Treatment Start Date) + 1 The cumulative dose of CPHPC will be calculated from the sum of the individual doses administered in each dosing session and over the study as a whole. Number of days of exposure to total anti-SAP mAb will be calculated as the number of doses administered. The cumulative dose of total aSAP mAb will be calculated from the sum of the individual doses administered (over all dosing sessions).

12.5.3. Safety

ECG Parameters
RR Interval

 IF RR interval (msec) is not provided directly, then RR can be derived as : [1] If QTcB is machine read & QTcF is not provided, then : $RR = \left[\left(\frac{QT}{QT_{cB}} \right)^2 \right] * 1000$ [2] If QTcF is machine read and QTcB is not provided, then: $RR = \left[\left(\frac{QT}{QT_{cF}} \right)^3 \right] * 1000$
Corrected QT Intervals

 IF RR interval (msec) is provided then missing QTcB and/or QTcF will be derived as : $QT_{cB} = \frac{QT}{\sqrt{\frac{RR}{1000}}} \qquad QT_{cF} = \frac{QT}{\sqrt[3]{\frac{RR}{1000}}}$

Non-Quantifiable Laboratory an Biomarker Values

 For laboratory values < lower limit of quantification: 
 the character value ('<x') will be listed; the numeric value will be imputed as half the limit of quantification (x/2) for figures and tables. For laboratory values > upper limit of quantification: 
 the character value ('>x') will be listed; the numeric value will be imputed as the limit of quantification (x) for figures and tables.

12.5.4. Triplicate ECG and Vital Sign measurements

ECG measurements are performed in triplicate at Screening and at the Day 1 Pre-dose timepoint of each dosing session. Vital signs are performed in triplicate at screening. The average of the triplicate measurements will be used for all summary tables, whereas individual measurements will be displayed in figures and listings. As a consequence, the average of the 3 Session 1 Day 1 Pre-dose measurements will be used as the baseline value for ECG summary tables. In case of missing Session 1 Day 1 Pre-dose ECG measurement, the average of the 3 Screening values will be used as the baseline value instead.

12.6. Appendix 6: Reporting Standards for Missing Data

12.6.1. Premature Withdrawals

Element	Reporting Detail
General	
 All available data from subjects who were withdrawn from the study will be listed and all available planned data will be included in summary tables and figures, unless otherwise specified.

12.6.2. Handling of Missing Data

Element	Reporting Detail
General	
 Missing data occurs when any requested data is not provided, leading to blank fields on the collection instrument: 
 These data will be indicated by the use of a “blank” in subject listing displays. Unless all data for a specific visit are missing in which case the data is excluded from the table. Answers such as “Not applicable” and “Not evaluable” are not considered to be missing data and should be displayed as such.
Outliers	
 Any participants excluded from the summaries and/or statistical analyses will be documented along with the reason for exclusion in the clinical study report.

Handling of Missing and Partial Dates

Element	Reporting Detail
General	Missing or partial dates will be displayed as captured in subject listing displays.
Adverse Events	
 The eCRF allows for the possibility of partial dates (i.e., only month and year) to be recorded for AE start and end dates; that is, the day of the month may be missing. In such a case, the following conventions will be applied for calculating the time to onset and the duration of the event: 
 Missing Start Day: First of the month will be used unless this is before the date of study drug first dose (earliest dose of GSK2315698 or anti-SAP mAb (labelled or unlabelled)); in this case the study treatment start date will be used and hence the event is considered On-treatment as per Appendix 3: Treatment States and Phases. Missing Start Time: 00:00 will be used unless the (possibly imputed) date is the date of study drug first dose for any treatment session; in this case the study treatment start time will be used and hence the event is considered On-treatment as per Appendix 3: Treatment States and Phases. Missing Stop Day: The last day of the month will be used (i.e. a '28', '29', '30' or '31' will be used for the day dependent on the month and year) or day of last follow-up assessment if earlier. Missing Stop Time: There will be no imputation of missing stop times. Completely missing start or end dates/times will remain missing, with no imputation applied. Consequently, time to onset and duration of such events will be missing. However, AEs will completely missing start dates/times will be assigned to the On-treatment phase and to the subject first treatment session, unless an on-treatment start can be ruled out from the end date/time (i.e. if the

Element	Reporting Detail
	AE ended prior to study treatment start date/time)
Concomitant Medications/ Medical History	
• Partial dates for any concomitant medications recorded in the CRF will be imputed using the following convention:
○ If the partial date is a start date, a '01' will be used for the day and 'Jan' will be used for the month○ If the partial date is a stop date, a '28/29/30/31' will be used for the day (dependent on the month and year) and 'Dec' will be used for the month.○ If the entire date is missing it is assumed that the concomitant medication occurred in all phases.• The recorded partial date will be displayed in listings.

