#### **9.1.1. Time Period and Frequency for Collecting AE and SAE Information**

- All AEs will be collected from the signing of the ICF until the final visit at the time points specified in the SoA (Section 2).
- All SAEs will be recorded and reported to the sponsor or designee immediately and under no circumstance should this exceed 24 hours, as indicated in [Appendix 4](#). The investigator will submit any updated SAE data to the sponsor within 24 hours of it being available.

- Investigators are not obligated to actively seek AEs or SAEs in former study subjects. However, if the investigator learns of any SAE, including a death, at any time after a subject has been discharged from the study, and he/she considers the event to be reasonably related to the study treatment or study participation, the investigator must promptly notify the sponsor.
- The method of recording, evaluating, and assessing causality of AEs and SAEs and the procedures for completing and transmitting SAE reports are provided in [Appendix 4](#).

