2. SUMMARY OF KEY PROTOCOL INFORMATION

The principal aim of this PET imaging study is to investigate the cardiac uptake of ⁸⁹Zr-GSK2398852 in patients with transthyretin amyloidosis restrictive cardiomyopathy (ATTR-CM), and its biodistribution to other organs.

This is an open-label non-randomised ⁸⁹Zr-GSK2398852 PET imaging study in clinically stable patients with either wild type or inherited ATTR-CM. Subjects will participate in up to two dosing sessions.

This study will be divided into two parts: Part A and an optional Part B.

All subjects will participate in a screening period of up to 35 days. Part A subjects (N=3) will participate in up to two dosing sessions approximately 26 days in duration (each). Part B subjects (N=3) will participate in one dosing session of approximately 26 days in duration. Total duration in the study will be approximately 3-4 months for Part A subjects, and approximately 2 months for Part B subjects.

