12.3. Appendix 3: Study Phases and Treatment Emergent Adverse Events

12.3.1. Treatment Phases

Treatment phases are defined for the purpose of AE summaries and listings.

AEs will be assigned to pre-treatment, on-treatment, and post-treatment phases according to the date/time of occurrence relative to Dates/Times of First and Last Doses of Study Drug.

Treatment Phase	Definition
Pre-Treatment	Date/Time of AE < First Dose Date/Time of Study Drug ¹
On-Treatment	First Dose Date/Time of Study Drug ¹ ≤ Date/Time of AE ≤ Last Dose Date/Time of Study Drug ² + 56 Days
Post-Treatment	Date/Time of AE > Last Dose Date/Time of Study Drug ² + 56 Days

¹Earliest dose of GSK2315698 or GSK2398852 or 89Zr-GSK2398852 in the study

²Latest dose of GSK2315698 or GSK2398852 or 89Zr-GSK2398852 in the study

Unless stated otherwise, AE summaries will only include AEs assigned to the on-treatment phase. All AE listings will include treatment phase assignment.

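### The missing-day rule for AE start dates moves partially dated events from a month before dosing onto the first-dose date and counts them as on-treatment

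*SAP*

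**What the plan says.** SAP 12.6.2 (Handling of Missing and Partial Dates, Adverse Events) notes that on the eCRF "the day of the month may be missing". For a missing start day the rule is "First of the month will be used unless this is before the date of study drug first dose". Where it is before, "in this case the study treatment start date will be used and hence the event is considered On-treatment as per Appendix 3". The companion rule for a missing start time then assigns the treatment start time to any event whose date, imputed or not, is a session's first-dose date.

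The same section treats a completely missing start date differently. That event also defaults to on-treatment, but "unless an on-treatment start can be ruled out from the end date/time". No such check on the stop date is attached to the missing-day rule.

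SAP 12.3.1 defines the pre-treatment phase as "Date/Time of AE < First Dose Date/Time of Study Drug" and adds: "Unless stated otherwise, AE summaries will only include AEs assigned to the on-treatment phase". SAP 12.3.3 computes duration as resolution date minus onset date plus 1.

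On when events can occur, Protocol 9.1.1 states "All AEs will be collected from the signing of the ICF until the final visit", and SAP Section 2 states "All subjects will participate in a screening period of up to 35 days".

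**The concern.** Setting an ambiguous start to the first-dose date is a reasonable cautious convention when the recorded month is the dosing month, because the event could have begun on either side of the first dose. For an earlier month there is no ambiguity: every day of that month precedes dosing. The rule nonetheless discards the recorded month and calls the event on-treatment, against the SAP's own phase definition.

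The result is also inconsistent within the section. An event with no start date at all is kept out of the on-treatment phase if its stop date precedes dosing. An event with a known earlier month and the same stop date is not.

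At stake are the AE summary tables (3.1 to 3.8, all on-treatment) and the phase, onset day and duration carried into the listings. SAP 12.3.3 also treats a blank causality field as drug-related, so a displaced screening event with missing causality would enter the drug-related table (3.4) too. Protocol 9.3.4.1 arranges monitoring before treatment so that background arrhythmias are not wrongly attributed to the antibody; this rule works against that aim.

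**Working it through.** The plan gives no figure to reproduce. The check is to apply the rule as written and then see how often its faulty branch can be reached.

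**1. The rule in logical form.** Let F be the first-dose date and M the first day of the recorded month.
- As written: start = F if M < F, otherwise M.
- If the recorded month is earlier than the month of F, then M < F always. The start is therefore F, the start time becomes the treatment start time, and the phase is on-treatment. No case escapes.

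**2. Worked example** (F = 10 March 2018, an illustrative date).

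| Recorded start | Start as written | Phase as written | Start with same-month condition | Phase with condition |
|---|---|---|---|---|
| Feb 2018, day missing | 10 Mar | On-treatment | 1 Feb | Pre-treatment |
| Mar 2018, day missing | 10 Mar | On-treatment | 10 Mar | On-treatment |
| Apr 2018, day missing | 1 Apr | On-treatment | 1 Apr | On-treatment |

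Only the February row changes. As written, its onset is Day 1.

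**3. Conflict with a known stop date.** Suppose the February event stopped on 20 February.
- As written: 20 Feb − 10 Mar + 1 = −18 + 1 = −17 days.
- If the stop day is also missing, it is imputed as 28 February: 28 Feb − 10 Mar + 1 = −10 + 1 = −9 days.
- With the condition and the 20 February stop: 20 Feb − 1 Feb + 1 = 20 days.

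**4. How far screening reaches into an earlier month.** If first dose falls on the 31st, 30 earlier days lie in the same month, so a full 35-day pre-dose window has at least 35 − 30 = 5 days in an earlier month (4 if the dosing day is counted among the 35). For the average case, every pre-dose day was enumerated for 365 first-dose dates and several window lengths:

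| Screening window (days) | First-dose dates whose window reaches an earlier month | Share of window days in an earlier month | Day-missing pre-dose AEs called on-treatment, as written | Same, with same-month condition |
|---|---|---|---|---|
| 7 | 23% | 13% | 100% | 87% |
| 14 | 46% | 25% | 100% | 75% |
| 28 | 92% | 48% | 100% | 52% |
| 35 | 100% | 58% | 100% | 42% |

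Reading the last two columns as shares of events assumes onsets spread evenly over the window. What remains in the final column is the genuine same-month ambiguity, which the condition deliberately leaves alone.

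**5. Effect on a table.** Part A has 3 subjects and both parts together have up to 6. One misassigned event adds at most 1/3 = 33 percentage points or 1/6 = 17 percentage points to an incidence. These are maximums: a subject already counted in that row adds nothing.

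**The case against.** The strongest case against is that this is a small drafting gap in a cautious default.

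- **Rarity.** Only events with the start day missing and a recorded month before the dosing month are misplaced. Fully dated screening events stay pre-treatment. Nothing indicates how often days will be missing, and with at most 6 subjects the count may be zero. This stands, and it limits the size of the problem.
- **Ascertainment.** The sentence in Protocol 9.1.1 goes on to tie collection to the Schedule of Activities, where the AE row appears to begin after the screening and baseline columns. Active questioning during screening is therefore less certain. Even so, collection is stated to start at consent, and the SAP defines a pre-treatment AE phase, so such events are expected.
- **Window length.** Screening lasts up to 35 days. A shorter one can lie wholly in the dosing month, where the rule is acceptable. This stands.
- **Visibility and reach.** Listings show partial dates as captured. The infusion-reaction listing is tied to the antibody infusion on Day 3, not to Day 1, and rash is flagged from an eCRF question. The PET endpoints are untouched and no hypothesis is tested. All true, but the summary tables and the derived phase, onset day and duration still carry the imputed date.
- **Direction.** The rule over-attributes events to treatment and cannot hide one. Caution justifies it where timing is unknown. It does not justify overriding a month that is known.

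**Conclusion.** The rule is wrong as written. For any event with a missing start day and a recorded month before the month of first dose, it replaces a known pre-treatment start with Day 1, contradicts SAP 12.3.1, puts the event into the on-treatment summaries, and can yield a negative duration. That follows from the wording alone and does not depend on the illustrative dates or the even spread of onsets.

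The expected number of affected events is small and cannot be estimated from the documents. The consequence per event is at most 33 percentage points in a 3-subject column or 17 in a 6-subject column. It should be corrected because it produces a demonstrably false classification in very small safety tables and is easily avoided.

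**What to change.** Reword the missing-start-day rule in SAP 12.6.2 along these lines: impute the first-dose date only if the recorded month and year are those of first dose and the stop date is not before first dose; otherwise impute the first of the recorded month.

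The consequences are:
- Earlier-month events become pre-treatment.
- Dosing-month events that stopped before first dose become pre-treatment.
- Other dosing-month events stay on-treatment, as now.
- Later-month events are unchanged.

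The first of the recorded month may fall before consent, but this does not affect the phase.

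The cost is one sentence in the SAP and one condition in the AE derivation. Data collection does not change, and the cautious default is kept wherever timing is truly ambiguous.

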12.7. Appendix 7: Values of Potential Clinical Importance

12.7.1. Haematology Values of Potential Clinical Importance

Haematology Analyte	Effect	Relative – Low (Multipliers of LLN)	Relative – High (Multipliers of ULN)
White Blood Cell Count		0.60	2.2
Neutrophil Count		0.60	2.2
Haemoglobin	Male	0.70	1.2
	Female	0.75	1.2
Platelet Count		0.70	2.50
Lymphocytes		0.60	

12.7.2. Chemistry Values of Potential Clinical Importance

Chemistry Analyte	Relative – Low (Multipliers of LLN)	Relative – High (Multipliers of ULN)
Albumin (mmol/L)	0.75	
Calcium (mmol/L)	0.80	1.20
Glucose (mmol/L)	0.60	2.00
Magnesium (mmol/L)	0.50	1.20
Potassium (mmol/L)	0.77	1.17
Sodium (mmol/L)	0.92	1.07
Creatinine (mmol/L)		1.6

12.7.3. Liver Function Test Values of Potential Clinical Importance

Liver Function Test Analyte	Effect	Potential Clinical Importance (PCI) Range	Unit
ALT/SGPT	High	>3x ULN	U/L
AST/SGOT	High	>3x ULN	U/L
AlkPhos	High	>3x ULN	U/L
T. Bilirubin	High	>2x ULN	µmol/L
T. Bilirubin + ALT	High	> 1.5x ULN T.Bilirubin + > 3x ULN ALT	µmol/L U/L

12.7.4. ECG Values and QTc Change of Potential Clinical Importance

ECG Parameter	Potential Clinical Importance Range (PCI)	Unit
Absolute QTc Interval	>500	msec
Increase from Baseline QTc	>60	msec
PR Interval	<110 and >220	msec
QRS Interval	<75 and >110	msec

12.7.5. Vital Sign Values and Changes of Potential Clinical Importance

VS Parameter	Potential Clinical Importance Range (PCI)	Unit
Systolic Blood Pressure	<90 and > 180	mmHg
Diastolic Blood Pressure	<30 and > 110	mmHg
Heart Rate	<35 and > 140	Bpm
Systolic Blood Pressure (Change from Baseline)	Increase >50	mmHg
	Decrease < 50	mmHg
Diastolic Blood Pressure (Change from Baseline)	Increase > 30	mmHg
	Decrease < 30	mmHg
Heart Rate (Change from Baseline)	Increase > 50	bpm
	Decrease < 50	bpm

